6.2.1. Rationale for Exclusion of Certain Study Candidates

Children younger than 2 years of age are excluded from this study due to the difficulty in obtaining a definitive diagnosis of UC in children/infants younger than 2 years of age and the potential for lack of efficacy in this age group. CCI

CCI

6.3. Lifestyle Restrictions

If applicable, study participants should be instructed not to donate blood or blood products during the study or for CCI following their last dose. In order to participate in the study, patients must agree to the contraception, reproduction, and breastfeeding criteria detailed in study entry criteria (Section 6.1 and Section 6.2).

6.4. Screen Failures

Allowed rescreening of patients after initial screen failure

Patients who have failed screening because of the following Inclusion/Exclusion Criteria may be rescreened when the reason for screen failure has resolved:

- [5]
- [6]
- [7]
- [8]
- [9]
- [11]
- [12]
- [15]
- [18c] (once polyps have been removed)
- [19]
- [22]
- [27] to [30]
- [35]
- [42]
- [45], and
- [46].

Individuals may be rescreened up to 2 times, for a maximum total of 3 screens unless additional rescreening is approved via sponsor's medical monitor or designee.

Participants who have failed screening because of Exclusion Criterion [21c] CCI may be rescreened 1 time (see Section 9.4.5.2).

Participants who have failed screening because of Exclusion Criterion [26] may be rescreened 1 time for *C. difficile* stool toxin. Additionally, a participant may be rescreened 1 time for stool culture or ova parasite. In either situation, participant rescreening should only occur after the reason for screen failure has resolved. It is recommended that the investigator confirms the participant has a negative *C. difficile* stool toxin/stool culture/stool ova parasite (as applicable) before performing additional rescreening investigations (see also Section 9.4.5.7). The interval between rescreening visits should be at CCI unless a shorter interval has been agreed with the study's medical monitor. Each time rescreening is performed the participant, parent/guardian must sign a new informed consent form (ICF) and will be assigned a new identification number.

Participants who screen fail because they are unable to complete their endoscopy prior to Visit 2 will not be required to undergo repeat TB testing, chest X-ray (CXR) or computed tomography (CT), HIV, HBV, and HCV testing stool cultures, and *C. difficile* testing if these were normal or negative during screening after discussion with sponsor medical monitor or designee. These tests should be repeated if based on the investigator's judgment the patient has risk factors and/or signs and symptoms of illness. Participants may undergo repeat rescreening sooner than CCI between screen failure and rescreening.

Disallowed rescreening of patients after initial screen failure

Patients who have failed screening because of the following Exclusion Criteria may **not** be rescreened:

- [10]
- [13]
- [14]
- [16]
- [18a] and [18b]
- [20]
- [21a] and [21b] (if current or past history of active TB)
- [23] to [25]
- [31] to [34]
- [36] to [41]
- [43], and
- [44].

6.4.1. Allowed Retesting of Screening Investigations

The screening investigations specified below may be retested once without the need for rescreening at the discretion of the investigator.

- **Screening hematology and chemistry blood tests:** where 1 or more results are outside the acceptable range for inclusion in the study but may be within the acceptable range for inclusion on retesting, due to test-retest variability.
- **Stool testing:** if there is a technical difficulty in performing or reporting the *C. difficile* or stool culture assays.
- **Retesting or confirmatory testing with an interferon- γ release assay (IGRA):** for example, QuantiFERON®-TB Gold or T-SPOT® assay) in selected patients as part of screening for LTBI (see Section 9.4.5.2 for details).
- **Endoscopy:** where the endoscopist is unable to adequately visualize the mucosa (for example, due to poor bowel preparation, technical issues with equipment) or where the central reader is unable to determine the centrally read Mayo ES (for example, failure of the recording equipment).

Retesting of all other screening investigations should be discussed with the medical monitor prior to retesting.

7. Treatments

7.1. Treatments Administered

In this study, mirikizumab is administered by IV or SC routes to pediatric patients in a staggered approach based on dose level as per [Table AMBU.3](#). Assignment to weight classes will be based on body weight at enrollment for induction period dosing and Week 12 for dosing at Week 12 and beyond; patients will continue in the assigned weight group throughout the duration of the study.

Patients in the high weight cohort will receive flat dosing, while patients in the low weight cohort will receive weight-tiered dosing in order to obtain similar exposures as flat dose regimens in the higher weight cohort.

Patients who achieve clinical response at Week 12 will follow the treatment regimens described in [Table AMBU.3](#). Patients who do not achieve clinical response at Week 12 will follow the treatment regimens described in [Table AMBU.4](#).

If any patient experiences loss of response and meets the criteria for loss of response in Section 9.1.5 at or after Week 16 and up to Week 40, they may receive rescue or discontinue the study based on their physician's discretion. Rescue treatment is IV mirikizumab Q4W for 3 doses based on their weight cohort. Once IV loss of response dosing is complete, patients who, in the opinion of the investigator, are receiving clinical benefit from mirikizumab therapy may continue with further SC dosing. Patients who are not considered by the investigator to be receiving clinical benefit from mirikizumab IV rescue therapy, will be discontinued and proceed to post-treatment follow-up.

Table AMBU.3. Treatment Regimens: Week 12 Clinical Responders

Weight Cohort	Dose Weeks 0, 4, and 8	Dose Weeks 12 through 48	Enrollment Initiation
>40 kg	300 mg mirikizumab IV	200 mg mirikizumab Q4W SC	CCI [REDACTED]
≤40 kg	5 mg/kg mirikizumab IV	≤20 kg: 50 mg mirikizumab Q4W SC >20 to ≤40 kg: 100 mg mirikizumab Q4W SC	CCI [REDACTED]
≤40 kg	10 mg/kg mirikizumab IV	≤20 kg: 50 mg mirikizumab Q4W SC >20 to ≤40 kg: 100 mg mirikizumab Q4W SC	CCI [REDACTED]

Abbreviations: IV = intravenous; PK = pharmacokinetics; Q4W = every 4 weeks; SC = subcutaneous.

Table AMBU.4. Treatment Regimens: Week 12 Clinical Nonresponders

Weight Cohort	Dose Weeks 0, 4, and 8	Dose Weeks 12 through 48
>40 kg	300 mg mirikizumab IV	[Redacted]
≤40 kg	5 mg/kg mirikizumab IV	
≤40 kg	10 mg/kg mirikizumab IV	

Abbreviations: IV = intravenous; Q4W = every 4 weeks; SC = subcutaneous.

Study Drug Administration

Intravenous infusion of mirikizumab will occur over at [Redacted] [Redacted]. All patients should be monitored for [Redacted] or longer following IV administration, according to investigator practice or local standard of care. Sites must have resuscitation equipment, emergency medications, and appropriately trained staff available during the infusion and monitoring period. Detailed instructions for investigational product administration will be provided separately by the sponsor.

Subcutaneous administration of mirikizumab will be given [Redacted]. Patients should be monitored according to investigator practice or local standard of care. Acceptable locations for SC administration include the abdomen, front upper thighs, upper arms, and buttocks.

The investigator or his/her designee is responsible for the following:

- Explaining the correct use of the investigational agent to the site personnel
- Verifying that instructions are followed properly
- Maintaining accurate records of investigational product dispensing and collection
- At the end of the study returning all unused medication to Lilly, or its designee, unless the sponsor and sites have agreed that all unused medication is to be destroyed by the site, as allowed by local law

7.1.1. Packaging and Labelling

Mirikizumab will be supplied to the investigator by Lilly or its designee. Clinical trial materials will be labeled according to the country’s regulatory requirements. All investigational products will be stored, inventoried, reconciled, and destroyed according to applicable regulations.

Clinical trial materials are manufactured in accordance with current Good Manufacturing Practices (GMP).

Study drug will be supplied as:

- Single use solution pre-filled syringe containing mirikizumab. The CCI syringe of mirikizumab is manufactured to deliver CCI
- Single use solution vial containing mirikizumab. The CCI vial of mirikizumab is manufactured to deliver CCI

Study drug will be provided with study-specific labels. Syringes and vials will be supplied in cartons, with the appropriate quantity specific to the planned dispensing schedule of the investigational product.

7.2. Method of Treatment Assignment

Study AMBU is open-label and patients will be assigned to mirikizumab dose groups based on weight at Visit 2.

An interactive web-response system (IWRS) will be used to assign investigational product to each patient. Site personnel will confirm that they have located the correct investigational product package by entering a confirmation number found on the package into the IWRS.

At Week 12, patients who meet the clinical response criteria (see [Table AMBU.5](#)) may proceed to the maintenance period and will continue with open-label mirikizumab SC dosing based on current body weight.

Nonresponding patients (see [Section 9.1.5](#)) may enter into extended induction dosing via IV administration for the next 12 weeks or discontinue the study.

7.2.1. Selection and Timing of Doses

Patients who meet all criteria will be assigned to treatment and will receive their assigned study drug as outlined in [Sections 7.1](#) and [7.2](#). The actual time of all dose administrations will be recorded in the patient's electronic case report form (eCRF).

7.3. Blinding

This is an open-label study.

7.4. Dosage Modification

Dose adjustments, other than CCI, are not permitted in this study.

7.5. Preparation/Handling/Storage/Accountability

The investigator or his/her designee is responsible for the following:

- Confirming that appropriate temperature conditions have been maintained during transit for all study drug received and any discrepancies are reported and resolved before use of the study drug.
- Ensuring that only participants enrolled in the study may receive study drug and only authorized site staff may supply or administer study drug. All study drugs must be stored in a secure, environmentally controlled, and monitored (manual or automated) area in accordance with the labeled storage conditions with access limited to the investigator and authorized site staff.
- The investigator, institution, or the head of the medical institution (where applicable) is responsible for study drug accountability, reconciliation, and record maintenance (such as receipt, reconciliation, and final disposition records).

Mirikizumab will be supplied by Lilly or its designee, in accordance with current GMP and will be supplied with lot numbers, expiry dates, and certificates of analysis, as applicable.

Mirikizumab should be stored in refrigerated conditions **CCI**.

Detailed instructions regarding supplies, preparation, and handling of mirikizumab will be provided by the sponsor.

7.6. Treatment Compliance

All doses of study medication will be administered at the study site by site personnel. Deviations from the prescribed dosage regimen should be recorded in the eCRF.

Every attempt will be made to select patients and caregivers who have the ability to understand and comply with study instructions. The investigator is responsible for discussing methods to ensure high treatment compliance with the patient and caregiver before study enrollment.

In particular, the investigator is responsible for ensuring that study participants and caregivers receive adequate training on and appropriate understanding of:

- the review of caregiver remission SF value as a critical data point
- how to evaluate their UC symptoms and to record them on the **CCI** diary, and
- the importance of being compliant with the **CCI** diary recording.

If a patient is noncompliant with study procedures and/or investigational product administration, the investigator should assess the patient to determine the reason for noncompliance and educate and/or manage the patient as appropriate to improve compliance. Overall compliance with therapy is defined in the statistical analysis plan (SAP). If, in consultation with Lilly or its designee, the noncompliance is deemed to be significant or if further noncompliance occurs, the patient may be discontinued from the study.

7.7. Concomitant Therapy

The list of prohibited medications and the list of permitted medications with dose stabilization guidance are provided in [Appendix 5](#) and [Appendix 6](#), respectively.

All concomitant medications (including medications for bowel preparations) taken during the study must be recorded in the Concomitant Medication eCRF. This includes concomitant medications for UC as well as for underlying conditions or diseases, and for AEs. All patients are encouraged to maintain their usual medication regimens for concomitant conditions or diseases throughout the study, unless those medications are specifically excluded ([Appendix 5](#)).

Stable doses of permitted UC concomitant medications (other than oral corticosteroids) are encouraged, unless dose modification is required due to AEs, or dose modification is otherwise specified in [Appendix 6](#). Patients taking oral corticosteroids are to follow the corticosteroid taper instructions described in Section [7.7.1](#).

Administration of prohibited UC medications for the management of symptoms of UC, approved or investigational, constitutes treatment failure. Use of such medications should not be withheld if, in the opinion of the investigator, failure to prescribe them would compromise patient safety. Patients who require a prohibited medication to treat their UC (see [Appendix 5](#)) need to be discontinued from study drug and complete an early termination visit (ETV) and post-treatment follow-up visits.

If a concomitant medication is needed to treat an AE or for appropriate medical management, the investigator should base decisions on patient and clinical factors. Local administration of corticosteroids (for example, intranasal, inhaled, intraarticular) are allowed as required for the management of pre-existing conditions and AEs. A patient who initiates a prohibited medication for a non-UC indication should be discussed with the medical monitor.

Patients are allowed to continue or initiate any concomitant medication for non-UC conditions, diseases, or AEs, insofar that the medication is not specifically prohibited ([Appendix 5](#)) and use of the medication complies with the dosing requirements as described in [Appendix 6](#).

7.7.1. Corticosteroid Taper

The investigator should use clinical judgement of the benefit/risk of steroid tapering for each individual subject as corticosteroids should be tapered as soon as possible following the recommended tapering regimen per local practice. Patients who enter Study AMBU on corticosteroid therapy for treatment of UC ^{CCI}

^{CCI} may initiate corticosteroid tapering based on the investigator's discretion. ^{CCI} who have not already begun tapering corticosteroid therapy should initiate corticosteroid tapering no later than ^{CCI} with mirikizumab will begin ^{CCI} is achieved at any time after starting ^{CCI}

Symptomatic response is defined as at least a ^{CCI} from baseline in the composite clinical endpoint of the sum of SF and RB subscores.

The recommended tapering schedule for oral corticosteroids (other than budesonide) is as follows:

CCI

CCI

CCI

In situations where the steroid tapering is paused, the tapering regimen (as described above) should be reinitiated within CCI of interruption of taper if possible, with a goal to complete tapering CCI

7.7.2. Vaccine Administration During the Study

Every effort should be made to vaccinate patients with standard of care vaccines prior to entry in the trial.

CCI

7.8. Treatment after the End of the Study

7.8.1. Study Extensions

Patients who complete this study through Week 52 and achieve clinical benefit may be eligible to participate in Study AMAZ. Patients who do not meet enrollment criteria for Study AMAZ or do not opt to continue into Study AMAZ, will be asked to complete the post-treatment follow-up period, as described in the Schedule of Activities (Section 2), which will complete their study participation.

7.8.2. Treatment after Study Completion

Mirikizumab will not be made available to patients after conclusion of the study, except through enrollment in the long-term extension trial, Study AMAZ.

7.8.3. Special Treatment Considerations

7.8.3.1. Premedication for Infusions

CCI [REDACTED] Any premedication for infusions or injections should be discussed with the medical monitor. Any premedication given should be documented as a concomitant therapy.

[figure not shown]
CCI [REDACTED]

Other Infusion-Related Events

If a patient experiences a reaction consisting of CCI [REDACTED] during or up to 6 [REDACTED] after an infusion of study drug, the following guidance should be followed:

CCI [REDACTED]

CCI

Injection Site Reactions or Infusion Site Reactions

If a patient experiences an injection site reaction or an infusion site reaction, such as pain, erythema, urticaria, pruritus, or angioedema localized to the SC injection or infusion site (in the absence of systemic hypersensitivity signs or symptoms), the following guidance should be followed:

CCI

8. Discontinuation Criteria

8.1. Discontinuation from Study Drug

8.1.1. Permanent Discontinuation from Study Drug

Study drug may be permanently discontinued during the study. Patients who discontinue study drug early will undergo early termination procedures, which include an ETV and post-treatment follow-up visits.

The investigator will also complete any AE reporting and follow-up that may be required (if applicable, see Section 9.2).

If a patient's study drug is discontinued before the end of the study, the patient should complete the ETV and post-treatment follow-up period as follows:

- Patients who discontinue investigational product during [redacted] will return for post-treatment follow-up visits (Visits 801 and 802) [redacted] after the end-of-treatment visit.
- Patients who discontinue study drug [redacted] will return for post-treatment follow-up visits (Visits 801 and 802) [redacted] after the end-of-treatment visit.

[figure not shown]
Possible reasons leading to permanent discontinuation of investigational product include the following (list is not exhaustive):

Patient Decision

- The patient or the patient's designee, for example, parents or legal guardian, requests to discontinue investigational product.

[redacted]

[redacted]

Disease Worsening

- The patient requires rescue therapy for exacerbation of UC at doses higher than those specified in the “dose stabilization” inclusion criterion (for example, prednisone **CCI** Inclusion Criterion [9]), or with medications specified in the “prohibited medications” exclusion criterion (for example, IV corticosteroids, infliximab, or IV cyclosporine; Exclusion Criterion [19]) (see also [Appendix 5](#)).

Safety Criteria for Study Drug Discontinuation

- The patient has a diagnosis of any of the following during the study:
 - Cancer other than squamous cell or basal cell carcinoma of the skin
 - Polypoid or non-polypoid dysplasia that is endoscopically visible or invisible
 - Active TB (see Section [9.4.5.2](#))
 - HIV/AIDS
 - Hepatitis B or development of detectable HBV DNA (see Section [9.4.5.4](#))
 - Hepatitis C or development of detectable HCV RNA (see Section [9.4.5.5](#)).
- The patient requires a colectomy during the study.
- The patient has a systemic hypersensitivity event or anaphylaxis to mirikizumab (Section [7.8.3.2](#)). Study drug should be discontinued after a systemic hypersensitivity event or anaphylaxis.
- The patient becomes pregnant. Pregnant patients **will not** undergo an endoscopy/flexible sigmoidoscopy at the ETV.
- The patient has absolute lymphocyte count **CCI** after retesting (see Section [8.1.2](#)).
- The patient is non-compliant with LTBI treatment (see Section [9.4.5.2](#)).
- The patient experiences an AE or SAE that, in the opinion of the investigator or sponsor, would preclude him/her from continuing to receive study drug or if they experience disease worsening that requires rescue therapy with protocol excluded medications.

Other Reasons for Study Drug Discontinuation

- The investigator determines that the patient is repeatedly noncompliant with study procedures and/or study drug (see Section [7.6](#)).
- Inadvertent enrollment (see Section [8.1.3](#)).

Patients discontinuing from the investigational product prematurely for any reason should complete AE and other follow-up procedures per Section 2 (Schedule of Activities), Section 9.2 (Adverse Events), and Section 9.4 (Safety).

8.1.2. Temporary Interruption (Withholding) of Study Drug

Some possible reasons for temporarily withholding the investigational product include (but are not limited to):

- Patient develops *C. difficile*, or other clinically important intestinal or extraintestinal infection during the study (including LTBI), see Section 6.2.
- Patient requires major surgery (administration of the investigational product may be restarted only after adequate wound healing).
- Patient develops a confirmed absolute neutrophil count [REDACTED]
- Patient develops absolute lymphocyte count [REDACTED] must be discontinued, if applicable, for a confirmed absolute lymphocyte count [REDACTED] (2 assessments below this threshold). The hematology must be repeated in [REDACTED]. If the absolute lymphocyte count remains [REDACTED], the hematology will be repeated again in [REDACTED] (that is, prior to the next dose of study drug). If the absolute lymphocyte count remains [REDACTED], the next dose of study drug will not be administered. The hematology will be repeated again in [REDACTED]. If the absolute lymphocyte count remains [REDACTED], study drug will be permanently discontinued. White blood cell and lymphocyte counts will be followed for these patients until they return to an acceptable level.
- The patient has other laboratory abnormalities that may lead investigator to hold the study drug until resolution of the abnormalities.

Cases that may merit temporary withholding of the study drug should be discussed with the medical monitor. The medical monitor, in consultation with the investigator, will determine when it is appropriate to recommence study drug.

8.1.3. Discontinuation of Inadvertently Enrolled Patients

If the sponsor or investigator identifies a patient who did not meet enrollment criteria and was inadvertently enrolled, then the patient should be discontinued from study drug, unless there are extenuating circumstances that make it medically appropriate for the patient to continue on study drug. If the investigator and the sponsor agree it is medically appropriate to continue, the investigator must obtain documented approval from the sponsor to allow the inadvertently-enrolled patient to continue in the study with or without treatment with the investigational product. Patients who are discontinued from study drug should have safety follow-up as outlined in Section 2 (Schedule of Activities), Section 9.2 (Adverse Events), and Section 9.4 (Safety), including ETV and post-treatment follow-up visits (Visit 801 and Visit 802).

8.2. Discontinuation from the Study

Patients will be discontinued (withdrawn) from the study in the following circumstances:

- Enrollment in any other clinical study involving an investigational product or enrollment in any other type of medical research judged not to be scientifically or medically compatible with this study
- Participation in the study needs to be stopped for medical, safety, regulatory, or other reasons consistent with applicable laws, regulations, and good clinical practices
- Investigator decision
 - The investigator decides that the patient should be discontinued from the study
 - If the patient, for any reason, requires treatment with another therapeutic agent that has been demonstrated to be effective for treatment of the study indication, discontinuation from the study will occur prior to introduction of the new agent
 - For patients who develop a condition, require a live vaccine, or begin a therapy that would have excluded entry into the study, the investigator must consult with Lilly-designated medical monitor to decide whether the patient can continue taking study drug and remain in the study.
- Patient decision
 - The patient or the patient's designee, for example, parents or legal guardian requests to be withdrawn from the study

Patients discontinuing from the study prematurely for any reason should complete AE and other safety follow-up specified per ETV, as outlined in Section 2 (Schedule of Activities), Section 9.2 (Adverse Events), and Section 9.4 (Safety).

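### Protocol 8.2 takes a child out of the study before another effective UC agent starts, which conflicts with 7.7, 8.1.1 and Appendix 5 and could cost the two post-treatment safety visits

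*Protocol*

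**What the plan says.** Four places in the protocol deal with a child who needs another UC treatment.

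- **8.2, Discontinuation from the Study.** The list opens with "Patients will be discontinued (withdrawn) from the study in the following circumstances". The second bullet under investigator decision covers a child who, whatever the reason, needs another agent shown to work in the study indication: "discontinuation from the study will occur prior to introduction of the new agent". The closing sentence asks for adverse event and other safety follow-up "specified per ETV, as outlined in Section 2 (Schedule of Activities), Section 9.2 (Adverse Events), and Section 9.4 (Safety"). It does not name Visits 801 and 802.
- **7.7, Concomitant Therapy.** Patients who need a prohibited drug for their UC "need to be discontinued from study drug and complete an early termination visit (ETV) and post-treatment follow-up visits". The same paragraph protects access to treatment: "Use of such medications should not be withheld if, in the opinion of the investigator, failure to prescribe them would compromise patient safety".
- **8.1.1, Permanent Discontinuation from Study Drug.** "Patients who discontinue study drug early will undergo early termination procedures, which include an ETV and post-treatment follow-up visits". Rescue with prohibited drugs for worsening UC, infliximab among the examples, is listed as a reason to stop study drug, and patients "will return for post-treatment follow-up visits (Visits 801 and 802").
- **Appendix 5.** Prohibited drugs may be used at the investigator's discretion once study drug has stopped and the ETV is complete. Withdrawal from the study is not a condition.

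The last paragraph of 9.2.1 removes the duty to look actively for adverse events once a patient has discontinued or completed the study, which it ties to completion of the disposition form.

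**The concern.** A child whose colitis worsens and who needs, say, infliximab falls under all four texts. Three of them treat the event as the end of study drug. The fourth treats it as the end of study participation, and fixes that end before the new drug is given. A site that follows 8.2 to the letter could close the child out after the ETV, at which point 9.2.1 no longer asks it to look for new adverse events.

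What is at stake is safety information in children who have recently stopped the antibody. The Schedule of Activities marks adverse event review and concomitant medication review at both Visit 801 and Visit 802. With about 30 children planned, each child's follow-up carries some weight.

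**Working it through.** No figure in the plan needs reproducing. The check is mainly a comparison of texts, with one small calculation.

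**Step 1: do the sections cover the same event?** Largely, but not exactly. The 8.2 bullet applies for any reason. 7.7 and the disease-worsening entry in 8.1.1 concern treatment of UC. A child switched to another UC agent because of worsening colitis is in all of them, and that is the case that matters here.

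**Step 2: what does each section ask for?**

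| Section | What stops | When the agent may start | Follow-up |
|---|---|---|---|
| 7.7 | Study drug | Not to be withheld where safety would suffer | ETV and post-treatment visits |
| 8.1.1 | Study drug | Not stated | ETV and Visits 801 and 802 |
| Appendix 5 | Study drug | After the ETV | ETV only is mentioned |
| 8.2 | Study participation | After leaving the study | As specified for the ETV, citing Section 2, 9.2 and 9.4 |

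**Step 3: can all of them be met?** Under 7.7, 8.1.1 and Appendix 5 the child stops study drug, has the ETV, starts the agent and attends Visits 801 and 802 while taking it. Under 8.2 the child must already be out of the study when the agent starts. Both can hold literally only if the agent waits until follow-up is over. No section asks for that, and the safety sentence in 7.7 points the other way.

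**Step 4: does the closing sentence of 8.2 settle it?** Not clearly. 8.1.1 ends with the same three references: patients "should complete AE and other follow-up procedures per Section 2 (Schedule of Activities), Section 9.2 (Adverse Events), and Section 9.4 (Safety"). The sentence in 8.2 differs in limiting follow-up to what is specified for the ETV. 8.1.1 and 8.1.3 name Visits 801 and 802; 8.2 does not.

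**Step 5: size per affected child.**

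- Visits at risk: 801 and 802, so 2.
- Stopping during IV dosing: Protocol 5.1 gives 16 weeks of post-treatment follow-up. 16 / 52 = 0.31 patient-years. This is a maximum, because 5.1 does not say when the 16 weeks start and the ETV may use part of them.
- Stopping during SC dosing: no figure. The timing in 8.1.1 is blacked out, and the 12 weeks in 5.1 are given for children who complete Week 52.
- Number of children: not given, and no switching rate is stated from which to derive one.

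**Step 6: which outputs are affected?** SAP 6.13 lists follow-up safety data for children who do not enter the extension study. SAP 6.13.2 restricts the adverse event tables to the Induction period and the combined Induction and Maintenance period. SAP 6.3.1 counts a child who permanently stops assigned treatment as a failure at all later time points, whatever happens at Visits 801 and 802. The main efficacy and adverse event tables therefore stay as they are; the exposure is the follow-up listing.

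**The case against.** The strongest reply is that the rules add up. A child withdrawn under 8.2 has also stopped study drug early, so 8.1.1 applies in its own right and requires the ETV and the post-treatment visits. 7.7 says the same for prohibited UC drugs. Nothing in 8.2 cancels either duty. Elsewhere the protocol describes early termination procedures as including post-treatment follow-up, so the closing sentence of 8.2 can be read as that whole package, and it points to the schedule in which Visits 801 and 802 stand. The protocol also uses discontinuing the study loosely for nonresponders and for loss of response.

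This stands as far as it goes. A reader might infer that the protocol leaves each site to choose, or that follow-up will be lost. The documents support neither, because 7.7 and 8.1.1 remain in force. The step through 9.2.1 also needs the disposition form to be completed at the ETV, and no visible text says that it is. The schedule notes are blacked out and might state who attends Visits 801 and 802. Finally, 9.2 still requires follow-up of known adverse events that are serious or otherwise medically important, related, or the cause of stopping study drug, and 9.2.1 still requires reporting of related serious events that the investigator learns of.

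The reply does not remove the conflict over order in Step 3. Adding the rules together keeps the visits, but it cannot make departure from the study before the new agent compatible with attending study visits while on it.

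**Conclusion.** The conflict is real and the bullet in 8.2 is wrong as written, but the point is minor. Its possible effect is the loss of active adverse event collection and of the planned assessments at two visits per switching child. For a child who stops during IV dosing that is at most 16 weeks, or 0.31 patient-years. This assumes that a site reads 8.2 literally and closes the child out at the ETV. The number of children affected is unknown and may be zero.

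A reader might also infer damage to the trial's results. For the main efficacy and adverse event tables the plan shows none. The schedule's PK row may carry a mark in the follow-up columns, but the column alignment of that table cannot be relied on here, so no claim about off-drug PK sampling is made.

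**What to change.** Reword the bullet in 8.2 where it stands, keeping its opening condition, so that the consequence reads:

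> the patient will be discontinued from study drug and complete the ETV before the new agent is introduced (treatment must not be withheld if this would compromise patient safety, per Section 7.7), and will remain in the study for post-treatment follow-up Visits 801 and 802, where applicable

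The change should stop there. Moving the bullet under disease worsening in 8.1.1 would misfile a rule that applies for any reason. Adding Visits 801 and 802 to the closing sentence of 8.2 would reach every withdrawal, including children who join another investigational study. The SAP needs no change.

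The cost is one reworded bullet. The visits and the reviews made at them are already planned, so no procedure is added. The downside is that follow-up data collected after the new agent starts are confounded by it and have to be read with that in mind.
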